### 13.4 Protocol Amendments

An amendment is a written description of change(s) to or formal clarification of a study protocol which may impact on the conduct of the clinical study, potential benefit of the clinical study, or may

affect subject safety, including changes of study objectives, study design, subject population, sample sizes, study procedures, or significant administrative aspects. An administrative change of a study protocol is a minor correction or clarification that has no significant impact on the way the clinical study is to be conducted and no effect on subject safety (e.g., change of telephone number(s), logistical changes). Protocol amendments must be approved by the Sponsor, health authorities where required, and the IRB/EC. In cases when the amendment is required in order to protect the subject's safety urgently, the amendment can be implemented prior to IRB/EC approval. Notwithstanding, the need for formal approval of a protocol amendment, the investigator is expected to take any immediate action required for the safety of any subject included in this study, even if this action represents a deviation from the protocol. In such cases, the Sponsor should be notified of this action, the IRB/EC at the study site, and, if required by local regulations, the relevant health authority) should be informed within 10 working days.

## APPENDIX 1 – HAK SCORE

### Prediction Rule for Estimating the Probability of Hospitalization Due to Pneumonia or Influenza and Death Due to Any Cause (Hak et al, 2004)

Characteristic	Score a
Age, years	
<70	0
70-74	14
75-79	28
80-89	42
≥90	56
Sex	
Female	0
Male	9
Outpatient visits during the previous year	
0	0
1-6	11
7-12	22
>13	33
Previous hospitalization due to pneumonia or influenza	
No	0
Yes	63
Comorbidityb	
Pulmonary disease	18
Heart disease	6
Renal disease or renal transplant	12
Dementia or stroke	22
Non-hematological and hematological cancer	48
Subject total score	
Notes:	
a The prognostic score for a given subject can be obtained by adding the scores for each applicable characteristic.	
b Pre-existing medical conditions of eligible subjects will be scored following a judgment by the investigator.	

## APPENDIX 2 – LIST OF ADVERSE EVENTS OF SPECIAL INTEREST

### Gastrointestinal disorders

- Celiac disease
- Crohn's disease
- Ulcerative colitis
- Ulcerative proctitis

### Liver disorders

- Autoimmune cholangitis
- Autoimmune hepatitis
- Primary biliary cirrhosis
- Primary sclerosing cholangitis

### Metabolic diseases

- Addison's disease
- Autoimmune thyroiditis (including Hashimoto thyroiditis)
- Diabetes mellitus type I
- Grave's or Basedow's disease

### Musculoskeletal disorders

- Antisynthetase syndrome
- Dermatomyositis
- Juvenile chronic arthritis (including Still's disease)
- Mixed connective tissue disorder
- Polymyalgia rheumatic
- Polymyositis
- Psoriatic arthropathy
- Relapsing polychondritis
- Rheumatoid arthritis
- Scleroderma, including diffuse systemic form and CREST syndrome
- Spondyloarthritis, including ankylosing spondylitis, reactive arthritis (Reiter's Syndrome) and undifferentiated spondyloarthritis
- Systemic lupus erythematosus
- Systemic sclerosis

### Neuroinflammatory disorders

- Acute disseminated encephalomyelitis, including site-specific variants (e.g., non-infectious encephalitis, encephalomyelitis, myelitis, radiculomyelitis)
- Cranial nerve disorders, including paralyses/paresis (e.g., Bell's palsy)
- Guillain-Barré syndrome, including Miller Fisher syndrome and other variants

- Immune-mediated peripheral neuropathies and plexopathies, including chronic inflammatory demyelinating polyneuropathy, multifocal motor neuropathy and polyneuropathies associated with monoclonal gammopathy
- Multiple sclerosis
- Narcolepsy
- Optic neuritis
- Transverse myelitis
- Myasthenia gravis, including Eaton-Lambert syndrome

#### Skin disorders

- Alopecia areata
- Autoimmune bullous skin diseases, including pemphigus, pemphigoid and dermatitis herpetiformis
- Cutaneous lupus erythematosus
- Erythema nodosum
- Morphoea
- Lichen planus
- Psoriasis
- Sweet's syndrome
- Vitiligo

#### Vasculitides

- Large vessels vasculitis including: giant cell arteritis such as Takayasu's arteritis and temporal arteritis
- Medium sized and/or small vessels vasculitis including: polyarteritis nodosa, Kawasaki's disease, microscopic polyangiitis, Wegener's granulomatosis, Churg–Strauss syndrome (allergic granulomatous angiitis), Buerger's disease thromboangiitis obliterans, necrotizing vasculitis and anti-neutrophil cytoplasmic antibody (ANCA) positive vasculitis (type unspecified), Henoch- Schonlein purpura, Behcet's syndrome, leukocytoclastic vasculitis

#### Others

- Antiphospholipid syndrome
- Autoimmune hemolytic anemia
- Autoimmune glomerulonephritis (including IgA nephropathy, glomerulonephritis rapidly progressive, membranous glomerulonephritis, membranoproliferative glomerulonephritis, and mesangioproliferative glomerulonephritis)
- Autoimmune myocarditis/cardiomyopathy
- Autoimmune thrombocytopenia
- Goodpasture syndrome
- Idiopathic pulmonary fibrosis
- Pernicious anemia
- Raynaud's phenomenon

Protocol Number: V200\_10  
Product Name: aQIVc  
Document Status: Final Version 1.0, Document Date: 30 Mar 2020

- Sarcoidosis
- Sjögren's syndrome
- Stevens-Johnson syndrome
- Uveitis

Protocol Number: V200\_10  
Product Name: aQIVc  
Document Status: Final Version 1.0, Document Date: 30 Mar 2020

SUSAR	Suspected Unexpected Serious Adverse Reactions
TFL	Tables, Figures and Listings
TOC	Table of Content

16 MAR 2021 Final Version 2.0

1. BACKGROUND AND RATIONALE

Vaccination is the primary method for preventing influenza and its severe complications. The efficacy in elderly individuals is lower due to the aging of the immune system and underlying medical conditions that can both increase the risk of influenza complications as well as interfere with immune response. The investigational vaccine in this study, MF59-Adjuvanted Quadrivalent Subunit Inactivated Cell-derived Influenza Vaccine (aQIVc), combines benefits of both cell-based, and adjuvanted technologies to meet the unmet need of influenza in older adults. The cell-derived antigen provides a better match to circulating strains, therefore addressing mismatch due to egg adaptation. The effect of inclusion of MF59 adjuvant to the vaccine is expected to enable increased magnitude of immune response by stimulating higher antibody responses at standard doses; increased breadth of immune response by expanding antibody repertoire, and increased duration of immune response with higher antibody response at 6 months after vaccination which is important in case of prolonged influenza seasons and/or late-season outbreaks.

For further details please refer to section 1.0 of the protocol.

This plan describes all details related to the statistical analysis of the data collected in the study V200_10 and is based on protocol version 30 March 2020.

This analysis plan is compliant with ICH Harmonized Tripartite Guideline, 5 February 1998, Statistical Principles for Clinical Trials, E9; World Health Organization, WHO Technical Report, Series No. 924. 2004, Annex 1: Guidelines on Clinical Evaluation of Vaccines: Regulatory Expectations; and FDA Center for Biologics Evaluation and Research (CBER) Guidance for Industry, May 2007, Clinical Data Needed to Support the Licensure of Seasonal Inactivated Influenza Vaccines.

16 MAR 2021 Final Version 2.0

2. OBJECTIVES

2.1 Primary Objective

2.1.1 Primary Immunogenicity Objective

To assess the immunogenicity of aQIVc in comparison with the QIVc, aQIV, and QIVr comparator vaccines as measured by HI assay^{*} using *cell-derived* target viruses at 28 days after vaccination, in subjects 50-64 and ≥65 years of age and overall (adults ≥50 years).

* In case of lack of agglutination for a specific strain using HI assay, immunogenicity for that strain will be assessed as measured by microneutralization (MN) assay as an acceptable alternative.

2.2 Secondary Objectives

2.2.1 Secondary Immunogenicity Objective(s)

- To assess the immunogenicity of aQIVc in comparison with the QIVc, aQIV, and QIVr comparator vaccines as measured by HI assay^{*} using *cell-derived* target viruses at 180 days after vaccination, in subjects 50-64 and ≥65 years of age and overall.
- 2. To assess the immunogenicity of aQIVc in comparison with the QIVc, aQIV, and QIVr comparator vaccines as measured by MN assay using *cell-derived* target viruses at 28 and 180 days after vaccination, in subjects 50-64 and ≥65 years of age and overall.

* In case of lack of agglutination for a specific strain using HI assay, immunogenicity for that strain will be assessed as measured by MN assay as an acceptable alternative.

2.2.2 Secondary Safety Objectives

- 1. To assess the reactogenicity of aQIVc as compared to QIVc, aQIV, and QIVr in subjects 50-64 and ≥65 years of age and overall for 7 days after vaccination.
- 2. To assess the safety of study vaccines in subjects 50-64 and ≥65 years of age and overall for 180 days after vaccination.

16 MAR 2021 Final Version 2.0

2.3 Exploratory Objectives

- 1. The immunogenicity of aQIVc in comparison with the QIVc, aQIV and QIVr comparator vaccines as measured by HI assay may be assessed using *egg-derived* target viruses at 28 days after vaccination, in subjects 50-64 and ≥65 years of age and overall.
- 2. To explore the comparability of the cell-based and egg-based titers as measured by HI assay and the association with the vaccine or other subject characteristics.
- 3. Additional exploratory immunogenicity analyses may be conducted to further characterize the immune response of aQIVc.

3. STUDY DESIGN

The study is a phase 2, stratified, randomized, observer-blind, multicenter study to evaluate the immunogenicity and safety of aQIVc influenza vaccine compared with three other influenza vaccines (aQIV, QIVc and QIVr) in subjects \geq 50 years of age.

Approximately 480 subjects \geq 50 years, 120 per vaccine group, will be randomized to receive either one of the four vaccines in 1:1:1:1 allocation ratio, stratifying according to age (\geq 50 to 64 and \geq 65 years), and previous vaccine history (previous 3 years yes or no). The distribution of all enrolled subjects across the two age subgroups should be about 50% in each. Approximately 40% of subjects in each age subgroup for each treatment group should not have been vaccinated with an influenza vaccine within the 3 previous influenza seasons.

Each subject will have two periods of study participation: Treatment Period (Day 1 to Day 29) and Follow-up Period (Day 30 to Day 181). The study procedures consist of three clinic visits (on Days 1, 29 and 181), and two safety phone calls on Days 7 and 91 (Table 1).

After an initial screening, subjects will be vaccinated with a single dose of aQIVc, aQIV, QIVc or QIVr on Day 1. All subjects will receive a Subject eDiary along with instructions to ensure proper completion and assessment on reactogenicity. Solicited AEs will be recorded daily for 7 consecutive days (or longer if the events are not resolved) following vaccination (Day 1 to Day 7).

16 MAR 2021 Final Version 2.0

Unsolicited AEs will be collected for 28 days after vaccination. SAEs, MAAEs, AEs leading to study withdrawal, and AESIs will be collected during the entire study period. These data will be captured by interviewing the subject during the clinic visits and safety phone calls and by review of available medical records. Subjects will be instructed to call the site in the event of any AE which they perceive as being of concern during the entire study period.

For further details please refer to section 3.0 of the protocol.

Statistical Analysis Plan, Protocol Number V200_10 16 MAR 2021 Final Version 2.0

Table 1 Time and Event Schedule

	Visit Type	Clinic Visit	Safety Phone Call	Clinic Visit	Safety Phone Call	Clinic Visit
	Study Day	1	7	29	91	181
Visi	t Window (Days)	n/a	-1/+3 day	-7/+3 days	+/-7 days	+/-7 days
	Visit Number	1	2	3	4	5
Study Event						
Study Treatment						
Vaccination		Х				
Screening and Safety						
Informed Consent		X ^a				
Medical History ^b		Х				
Pregnancy test ^c		Х				
Physical Exam		Х				
Targeted Physical Exam ^d		Х		Х		Х
Measuring body temperature		Х				
Exclusion/Inclusion Criteria		Х				
Randomization		Х				
30 Minutes Post Injection Assessment		Х				
Train and Dispense Subject eDiary		Х				

16 MAR 2021 Final Version 2.0

	Visit Type	Clinic Visit	Safety Phone Call	Clinic Visit	Safety Phone Call	Clinic Visit
	Study Day	1	7	29	91	181
Visi	t Window (Days)	n/a	-1/+3 day	-7/+3 days	+/-7 days	+/-7 days
	Visit Number	1	2	3	4	5
Study Event			•		•	
Review of eDiary data and compliance		On	going during eDiary	use		
Assess unsolicited AEs		Х	Х	Х		
Assess SAEs		Х	Х	Х	Х	Х
Assess for AEs leading to withdrawal, medically attended AEs and AESIs		Х	Х	Х	Х	Х
Assess relevant medications and vaccinations		Х	Х	Х	Х	Х
Immunogenicity						
Serology blood draw		Х		Х		Х
Study Completion/termination						Xe

Notes: ^a Consent form(s) should be signed prior to performing any procedures. The informed consent process may be conducted earlier, but within 10 days prior to Day 1. ^b Medical history includes existing comorbidities. ^c A pregnancy test should be done for females of childbearing potential in order to rule out any pregnancy. ^d Based on specific complaints as indicated by the subject. ^e Subjects who terminate the study early will be requested to complete all safety-related Study Completion procedures. Abbreviations: AE = adverse event; AESI = adverse event.

16 MAR 2021 Final Version 2.0

4. RANDOMIZATION AND BLINDING

4.1 Method of Group Assignment and Randomization

Approximately 480 subjects \geq 50 years will be randomized to receive either aQIVc or one of 3 comparator vaccines in a 1:1:1:1 allocation ratio, stratifying according to age (50 to 64 and \geq 65 years) and previous vaccination (in 3 years before yes versus no). The number of subjects randomized will be an equal split between the age subgroups. Approximately 40% of subjects in each age subgroup for each treatment group should not have been vaccinated within the 3 previous influenza seasons.

The subject will be randomized in the IRT/RTSM system. The subject will receive a unique Subject ID that will be used for all eCRFs and associated study documentation for the duration of the study. The list of randomization assignments is produced by the service provider (IQVIA) and approved by the Sponsor according to the applicable Sponsor's Standard Operating Procedure (SOP).

4.1.1 Definition of Randomization/Vaccination Errors

The list below provides categories for errors that may occur during vaccination.

Randomization errors:

• Administered wrong kit (subject was vaccinated with a vaccine different from the one assigned at randomization).

Vaccination errors:

- Administered only part of the study vaccine.
- Incorrect vaccine location.
- Administered expired vaccine.
- Administered temperature deviated vaccine.

Stratification error:

• Subject randomized in the wrong stratification stratum.

16 MAR 2021 Final Version 2.0

Randomization and Vaccination errors are considered as major (CSR-reportable) protocol deviations. Stratification errors will not be considered as CSR-reportable PDs as there will no impact on the actual dose administered. Subjects will be included in analysis according to actual age subgroup and actual previous vaccination history.

4.1.2 Forced Randomization

Forced randomization will not be utilized in this trial

4.2 Blinding and Unblinding

The study is designed as an observer-blind study. Unblinded teams will be used for preparation of the safety reports for the Independent Safety Team (IST) and Data Monitoring Committee (DMC).

If a subject is unblinded during the study, it is to be documented as a as CSR-reportable PD, except for subjects unblinded by Pharmacovigilance due to suspected unexpected serious adverse reactions (SUSAR). The unblinding will be documented appropriately. The unblinded subject(s) are excluded from the PPS. Unblinded subjects will be included in the FAS and safety sets.

A final analysis on the primary and the secondary objectives including all immunogenicity and safety data collected up to including the Day 29 Visit will be conducted on cleaned and locked data. Access to information about study groups will be limited by biostatisticians and programmers in charge of statistical analysis. No individual listings and unblinding data will be generated at this stage until the completion of the study.

5. SAMPLE SIZE AND POWER CONSIDERATIONS

This study is an exploratory Phase 2 study without any formal hypothesis testing. The total sample size of 480 subjects has been determined by the feasibility of conducting the study in one season.

This sample size of n=108 per vaccine group – assuming 10% drop-out rates – is enough to obtain preliminary immunogenicity data.

For example, assuming a SD of log10-transformed HI titres as 0.45:

16 MAR 2021 Final Version 2.0

- In pairwise dose-group comparisons with n=108 per dose group it would be feasible to detect a difference of 1.49 in the GMT ratio with statistical power of 80% with the two sample T-test at significance level of 0.05.
- With n=108 per dose group; the precision of the GMT ratio expressed as 95% CI will be from 0.76 to 1.32 multiplied by the observed GMT estimate.

Table 2 illustrates the effects which can be detected depending (80% power and the two-sided significance level of 0.05) on different values for the inter-subject variation, as well as the size of the 95% two-sided confidence interval indicating the precision of the GMT ratio estimates.

For example, assuming a SD of log10-transformed HI titres as 0.45:

- In pairwise dose-group comparisons with n=108 per dose group it would be feasible to detect a difference of 1.49 in the GMT ratio with statistical power of 80% with the two sample T-test at significance level of 0.05.
- With n=108 per dose group; the precision of the GMT ratio expressed as 95% CI will be from 0.76 to 1.32 multiplied by the observed GMT estimate.

 Table 2 Detectable GMT ratios (80% power, 5% two-sided test)

SD #	Log10 GMT Differences that can be detected	GMT ratios can be detected	95% confidence interval (times the GMT ratio)
0.45	0.172	1.49	0.76 to 1.32
0.50	0.191	1.55	0.73 to 1.36
0.55	0.211	1.62	0.71 to 1.40
0.60	0.230	1.70	0.69 to 1.45
0.65	0.250	1.77	0.67 to 1.49
0.70	0.268	1.85	0.65 to 1.54
0.75	0.287	1.94	0.63 to 1.59
0.80	0.306	2.02	0.61 to 1.64

Notes: # range of values of the standard deviation of the log10 titers based on studies V7P38 and V70P3 (data on file). Abbreviations: GMT= geometric mean titer. SD = Standard deviation.

6. DETERMINATION OF PROTOCOL DEVIATIONS

6.1 Definition of Protocol Deviations

CSR reportable PD are defined in accordance with International Conference on Harmonization (ICH) E3 as important PDs related to study inclusion or exclusion criteria, conduct of the trial, subject management or subject assessment resulting in the potential to jeopardize the safety or rights of the trial subjects or the scientific value of the trial. Protocol deviations will be classified as CSR-reportable and non-CSR-reportable.

Seqirus's standard Protocol Deviation Specification Document lists all the pre-specified observable and programmable PDs, including their classification, categories, sub categories and impact on the analysis.

CSR reportable PDs may lead to exclusion of the subject or part of the subject's data from at least the PP analysis set.

The number of subjects in any and by PD category will be summarized by study treatment and overall. Individual subject listings will be provided sorted by subject and by PD category.

Prior to unblinding, all reportable PDs will be evaluated, and designated study staff will develop a memo that describes the PDs that led to exclusions from analysis sets. This memo will be signed off by at least the Biostatistician and the Clinical Program Director (CPD) and will be included in the trial master file.

6.2 Determination of Protocol Deviations

The source/method of identification can be either observable or programmable. Programmable PDs are those which can be programmed from the data recorded in the clinical database. Observable PDs are identified by CRAs during monitoring or other team members.

A set of listings will be programmed following the Protocol Deviation Specification List to determine and categorize the protocol deviations. These listings will be provided for review on an ongoing basis during the study.

This review will also include protocol deviations captured reported in monitoring reports. After the review, the Clinical Program Director and the Global Clinical Operation Lead will provide the Biostatistician with:

16 MAR 2021 Final Version 2.0

- An assessment of CSR reportable PDs based on blinded clinical data review.
- An assessment of subjects without PDs (e.g., premature withdrawals due to adverse event, withdrawal of consent) who should be excluded from an analysis set.

7. ANALYSIS SET

7.1 All Enrolled Set

All screened subjects who provide informed consent and provide demographic and/or other baseline screening measurements, regardless of the subject's randomization and vaccination status in the trial and receive a subject identification (ID).

Demography and baseline characteristics tables as well as subject listings will be produced on the All Enrolled Set.

7.2 All Exposed Set

All subjects in the All Enrolled Set who received a study vaccination.

7.3 Full Analysis Set (FAS), Immunogenicity

All subjects in the All Enrolled Set who are randomized, received study vaccination and provided immunogenicity data on Day 1 and Day 29 assessment.

In case of vaccination error, subjects in the FAS sets will be analyzed "as-treated" (i.e., according to the vaccine the subject received).

If a subject is unblinded before the completion of the Day 29 visit, he/she will be included in the FAS.

7.4 Per Protocol Set (PPS), Immunogenicity

All subjects in the FAS Immunogenicity who:

- Correctly receive the vaccine (i.e., receive the vaccine to which the subject is randomized).
- Have no CSR-reportable PD leading to exclusion (i.e. impacting the results) as defined prior to unblinding.
- Have immunogenicity assessments within the window of +/- 7 days around the Day 29 visit, and Day 1 sample taken within 3 days before vaccination.

If a subject receives a vaccine, labelled for another subject but the same as the one the subject was randomized to, the subject will not be removed from the PPS. If a subject is unblinded during the study (except for SUSAR), he/she will be excluded from the PPS.

7.5 Safety Set

Solicited Safety Set

All subjects in the All Exposed Set with any solicited adverse event data collected on the electronic diary, including temperature measurements or use of analgesics/antipyretics.

Unsolicited Safety Set

All subjects in the All Exposed Set with results of the unsolicited adverse event assessments recorded. A record of safety assessment performed at a specific time point, with confirmation of no AE, is considered as adverse event data hence subject is to be included.

Overall Safety Set

All subjects who are in the Solicited Safety Set or in the Unsolicited Safety Set.

Subjects will be analyzed as "treated" (i.e., according to the vaccine a subject received, rather than the vaccine to which the subject may have been randomized).

7.6 Other Analysis Set

For the analysis of the immunogenicity data collected at Day 181 assessment, subsets of the FAS and PPS, immunogenicity will be used. Subjects will be only included if there was Day 181

16 MAR 2021 Final Version 2.0

immunogenicity data collected and disallowed concomitant medication impacting the results was not used.

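### The Day 181 immunogenicity sets inherit a Day 29 sample requirement that the Day 181 endpoints do not use, and they state no analysis window for the Day 181 sample

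*SAP*

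**What the plan says.** SAP 7.6 sets the populations for the six-month titres: "For the analysis of the immunogenicity data collected at Day 181 assessment, subsets of the FAS and PPS, immunogenicity will be used". It then adds two conditions and no others: "Subjects will be only included if there was Day 181" "immunogenicity data collected and disallowed concomitant medication impacting the results was not used".

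The parent sets are defined around Day 29. Under SAP 7.3, FAS subjects must have "received study vaccination and provided immunogenicity data on Day 1 and Day 29 assessment"; no day range is attached. SAP 7.4 adds, for the PPS: "Have immunogenicity assessments within the window of +/- 7 days around the Day 29 visit, and Day 1 sample taken within 3 days before vaccination".

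Protocol 8.4.3.2.2 makes the PPS the set for all secondary immunogenicity objectives. It names interfering concomitant medication as the ground for extra Day 181 exclusions, and adds an FAS analysis only if more than 10% of subjects are excluded. SAP 7.6 names both sets without repeating that trigger.

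The visit schedule (protocol Table 0-1, SAP Table 1) allows 7 days either side of Day 181. No analysis-set definition in either document refers to that window.

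**The concern.** Antibody level at six months is a secondary objective in SAP 2.2.1, by HI and by MN, and longer persistence is part of the vaccine's stated rationale (protocol 1.1, SAP 1). The set used for that comparison should depend on the samples that enter it. Instead, entry depends on attendance at Visit 3 and, for the PPS, on its timing.

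Two things are at stake. Usable six-month data can be discarded. The subjects who remain are also selected on a post-randomisation event with no role in the Day 181 estimate, in an analysis that SAP 8.2 already limits to complete cases under a missing-completely-at-random assumption. Separately, the set definitions do not tell a reader whether a sample taken on, say, Day 200 counts as a Day 181 value in the PPS.

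**Working it through.** **1. Which titres the Day 181 analysis needs.** SAP 11.3 lists the HI endpoints at Day 181 as GMT, fold increase over Day 1 and the percentage at or above 1:40. For MN at Day 181 it lists GMT and fold increase over Day 1. The model in SAP 8.1 adjusts for the pre-vaccination titre, age subgroup and vaccination history. Seroconversion is defined at Day 29 only. No Day 181 quantity uses a Day 29 titre.

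**2. Who is in and who is out.** Take subjects with a valid Day 1 sample, the correct vaccine, no disallowed medication and no other exclusionary deviation. The PPS window around Day 29 is Day 22 to Day 36; the scheduled Day 181 window is Day 174 to Day 188.

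| Day 29 sample | Day 181 sample | Day 181 FAS | Day 181 PPS |
|---|---|---|---|
| None | In window | Out | Out |
| Day 38 | In window | In | Out |
| In window | After Day 188 | In | Not excluded by the stated timing rules; depends on the deviation specification |

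**3. Whether such subjects can arise.** Under protocol 4.5, the lost-to-follow-up procedure starts with a missed Study Completion visit or three consecutive missed contacts. A subject who misses only Visit 3 can stay in the study and give a Day 181 sample.

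**4. Whether the FAS fallback helps.** It can bring back the Day 38 subject, if the 10% trigger is met. It cannot bring back a subject with no Day 29 titre, because the FAS requires one.

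**5. Size.** Reproduce the plan's precision first. SAP 5 gives n = 108 per group (120 × 0.9), SD 0.45 on the log10 scale, and a 95% interval of 0.76 to 1.32 times the GMT ratio.

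- Half-width = t(0.975, 214) × SD × √(2/n) = 1.971 × 0.45 × √(2/108) = 0.1207.
- 10^−0.1207 = 0.757 and 10^0.1207 = 1.320. This agrees with the SAP.

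The documents do not say how many subjects would have a Day 181 sample but a missing or mistimed Day 29 sample. Two assumed scenarios show the range.

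*Recovery.* Suppose 108 per arm remain under the present rule, and 3 to 6 of the 12 lost (120 × 10%) have usable Day 181 samples.

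- n = 111: √(108/111) = 0.986, so the log-scale interval is 1.4% narrower. The upper factor is 10^(0.1207 × 0.986) = 1.315.
- n = 114: √(108/114) = 0.973, so it is 2.7% narrower. The upper factor is 10^(0.1207 × 0.973) = 1.311.

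*Loss.* Suppose instead that 108 per arm give Day 181 samples and the Day 29 condition removes some of them.

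| Removed | n per arm | 95% CI factor, SD 0.45 |
|---|---|---|
| 0% | 108 | 0.757 to 1.320 |
| 2% | 106 | 0.755 to 1.324 |
| 5% | 103 | 0.752 to 1.329 |
| 10% | 97 | 0.746 to 1.341 |

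At SD 0.80, a 10% loss moves the upper factor from 1.639 to 1.685. Within an age subgroup (about 54 per arm, SD 0.45), a 10% loss (n = 49) moves it from 1.485 to 1.515. Under every assumption the effect on precision is small.

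**The case against.** The SAP follows the protocol, which evaluates Day 181 on the PPS less further exclusions, so the documents do not conflict. Nested sets keep the Day 29 and Day 181 tables on the same subjects, which helps when reading persistence. The study is exploratory, with no hypothesis tests or success criteria, so no error rate or pre-specified decision changes. SAP 8.2 also describes reasons for missing titres by group, compares baseline characteristics of subjects with and without data, and considers sensitivity analysis if more than 10% are missing. All of this stands, and it limits the weight of the point. It does not supply a reason for a Day 181 estimate to require a Day 29 titre.

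A reader might infer that both Day 181 sets require an in-window Day 29 sample. They do not: only the PPS has the window, and the Day 38 subject stays in the FAS.

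A reader might also infer that late Day 181 samples will be kept in the PPS. The documents do not establish that. SAP 7.4 excludes subjects with an exclusionary CSR-reportable deviation, and SAP 6.1 places the list of deviations and their effect on analysis in a separate document that was not supplied. That document may cover Day 181 timing. What can be said is that the SAP writes timing rules for the Day 1 and Day 29 samples into the PPS definition and writes none for Day 181.

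The assumed 3 to 6 recovered subjects per arm have no support in the documents. The SAP calls the 10% drop-out and protocol 8.5 calls it exclusions; true drop-outs would not return at Day 181.

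**Conclusion.** The point holds as a cheap improvement to the set definitions. As written, SAP 7.6 removes subjects with valid Day 1 and Day 181 samples from both Day 181 sets if the Day 29 sample is missing, and from the main set if it is mistimed. Neither exclusion serves the Day 181 endpoints.

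The size is small and conditional: a log-scale interval about 1.4% to 2.7% narrower if 3 to 6 subjects per arm are recovered. A bias in the GMT ratio is not shown, because nothing in the documents indicates that Visit 3 attendance differs between arms in a way linked to titre. The benefit is the removal of an unnecessary selection step.

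The unstated Day 181 window is a gap in detail and would not carry the point alone. Its effect on the GMTs cannot be sized, because the documents give neither a waning rate nor an expected number of late samples.

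**What to change.** In SAP 7.6, define the Day 181 sets on their own samples:

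- **FAS-Day 181:** randomised, vaccinated, with Day 1 and Day 181 titres; no Day 29 requirement.
- **PPS-Day 181:** the same, plus the correct vaccine, no exclusionary deviation relevant to Day 181, and a Day 181 sample within the scheduled 7 days either side.
- Report by arm how many subjects enter each set without a Day 29 titre.

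SAP 7.6 currently applies the disallowed-medication condition to both subsets. Under this wording it would act through the deviation rule in the PPS. If the sponsor wants it in the FAS as well, the text should say so.

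The deviation specification should be checked for a Day 181 timing rule so that the two documents agree. Because protocol 8.4.3.2.2 refers to the PPS as defined there, the change should be recorded in SAP 16.

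The cost is SAP wording and one extra set flag. The downside is that the Day 29 and Day 181 tables are no longer strictly nested; the count of subjects without a Day 29 titre shows how far they differ.
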